Summary. This overview demonstrates that: 1) low-grade inflammation in MetS is attributed to endotoxemia in association with poor gut barrier integrity, 2) endotoxemia is causally-related to the initiation of obesity and insulin resistance³⁵ and circulating endotoxin is prognostic of progressive liver function deterioration,³⁶ 3) MFGM constituents provide antiinflammatory and prebiotic activity at the gut and attenuate endotoxemia, and 4) increased SCFAs from commensal bacteria of the gut not only improve gut integrity, but also promote intestinal incretin secretion to help manage glucose intolerance. Thus, our translational studies in MetS persons are expected to provide novel evidence that MFGM exhibits antiinflammatory activity to enhance glucose tolerance by attenuating endotoxemia. These findings would be of *significance* to public health because could they help to establish that dietary fat "quantity" is not necessarily detrimental to MetS risk, but rather fat "quality" potentiates host health due to enhanced gut barrier function. This would lead to evidence-based recommendations to help reverse course of dietary trends indicating that dairy consumption decreases in an age-dependent manner and that ~90% of Americans fail to meet the daily recommended intake of dairy.³

Anticipated Results

We expect the intervention to result in high compliance (>95%), consistent with our rigorous approach to provide all foods and test beverages.

In *Obj 1*, MFGM is *expected* to time-dependently decrease serum endotoxin (i.e. d 0 to d 14), and lower day 14 endotoxin compared with coconut and palm oil-enriched milk. MFGM will also attenuate meal challenge-induced increases in gut-derived endotoxemia. These benefits will correlate with improved gut barrier function as indicated by: 1) decreased urinary recovery of sugar probes (i.e. increased gut integrity), 2) increased fecal SCFA levels; these potentiate intestinal junction protein expression,²⁸ and 3) an alleviation of gut dysbiosis (e.g. microbial diversity, *Firmicutes:Bacteroidetes* ratio). Indeed, we expect reduced gut bacteria abundance. This is important because intestinal bacteria overgrowth provokes metabolic disease.^{37,38} Likewise, MFGM-mediated

prebiotic effects are anticipated to increase commensal bacteria (e.g. butyrate producers) and its anti-microbial activities are expected to reduce pathogenic populations (e.g. pyrogenic bacteria, decreased LPS synthesis).

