Our “whole food” approach that matches nutrient profiles between study arms will maximize translation of the benefits of full-fat milk that are driven, at least in part, by MFGM. The dose of MFGM at 10-times that in whole milk also reflects that consumers obtain MFGM from dairy foods other than milk. As major outcomes, we expect to demonstrate novel evidence that MFGM-enriched dairy milk decreases metabolic endotoxemia and improves glucose tolerance in MetS adults by increasing gut barrier integrity in association with alleviating gut dysbiosis and inflammation. This will be of *significance* because MetS affects ~35% of Americans,⁴⁸ and is driven by inflammation attributed to poor gut health that leads to excess absorption of bacterial endotoxins. Thus, dietary management of endotoxemia with dairy milk could significantly impact the incidence of MetS while helping to explain outcomes of observational studies suggesting benefits of full-fat milk for weight management.⁴⁹ Ultimately, this study could help to debunk long-standing dogma that targets full-fat

dairy for energy reduction⁵⁰ and support evidenced-based recommendations as part of forthcoming *Dietary Guidelines for Americans*.

III. Procedures

A. Study Design

We will enroll male and female MetS adults (n = 24; 18-65 y) to complete a *2-arm, double-blind, randomized controlled, crossover trial*. They will be randomized in 4-unit blocks to receive, for 14 d, a controlled diet with dairy milk (3.5% fat; 3 servings/d) enriched with MFGM-derived phospholipid or a matched dairy milk that instead contains coconut and palm oil (control). We will provide *all* foods during each study period to ensure weight maintenance and to increase homogeneity of gut and host responses (see *Dietary Control*).

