
Power Calculation and Data Analysis. [name] (biostatistician; see *Letter of Support*) performed a power analysis using endotoxin (d 14) as the primary outcome. No human studies have examined MFGM on endotoxemia. Thus, we used our data from MetS and healthy persons in which fasting endotoxin was measured 5-times at 2-wk intervals. On average, endotoxin was >2-times higher in MetS ($P<0.0001$), and did not differ ($P>0.4$) by time or gender. We then calculated the mean difference in endotoxin between healthy and MetS subjects (16.4 ± 7.8 vs 32.4 ± 4.4 EU/mL, CV =48% vs 15%). Power analysis indicated that only 8 subjects/group would be required to obtain 95% power ($\alpha = 0.05$) using the larger of the two CVs. For the proposed study in only MetS persons, we estimated that MFGM would result in a conservative improvement of 60% of the difference in endotoxin in the MFGM vs control phases: $((32.4-16.4) \times 0.6 = 9.6$ EU/mL); CV = 32% (SD = 10.4). Thus, we would have ~90% power ($\alpha = 0.05$) with 14 MetS persons completing both study arms. Our targeted enrollment of 24 MetS persons (12F/12M) is therefore expected to be powered strongly to examine MFGM on endotoxemia. This will also account for attrition (estimated at 10%) and provide sufficient power to consider gender x treatment interactions.

Most data will be analyzed by linear mixed effects models with random effect for subjects (to account for repeated measures) and fixed effects for treatment, gender, time period, and their interactions. Multivariate regression will define correlations between variables with consideration of potential covariates. Significance for all analyses will be set at $P<0.05$.

C. Measurement/Instrumentation

Anthropometric Parameters and Blood Pressure. At screening, day 0, 7, and 14, participants will rest for 15 minutes prior to determining blood pressure using an automated cuff. BMI will be calculated from height determined from a wall-mounted stadiometer and weight from a calibrated scale. Waist circumference will be assessed at the level of the umbilicus using a nonflexible measuring tape.

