Microbiota Composition. Microbiota composition will be assessed from fecal samples collected on d 13 of each study period. Samples will be extracted in the [name] lab, and genomic sequencing will be performed in the OSU MCIC core lab (see *Facilities*) using routine procedures. In brief, effects due to MFGM on total bacterial abundance will be assessed using qPCR (i.e. to assess intestinal bacteria overgrowth).⁵⁹ Microbiota of each sample will be characterized for diversity and community structure by sequencing 16S rRNA genes using MiSeq. Bioinformatic analysis will be performed using Qiime⁶⁰ and bacteria identified by comparing each operation taxonomic unit (OTU) to RDP and Silva databases.^{61,62} α -Diversity (OTU richness, Shannon-Wiener diversity index, evenness) will be calculated using Qiime and β -diversity using the Bray-Curtis dissimilarity,⁶³ followed by multivariate analysis (i.e. PCA, PERMANOVA, ANOSIM, PLS-DA) to determine MFGM effects.

The functional metagenome will be predicted using PICRUSt⁶⁴ and PanFP⁶⁵ based on reference databases and the KEGG Orthology classification scheme to obtain a functional gene abundance matrix.

We will validate preclinical findings showing increased microbiota potential to generate SCFAs in response to MFGM.^{30,31,47} These gut health-promoting metabolites (butyrate, acetate, propionate) will be quantified by LC-MS as we described,⁵⁷ with modification,⁶⁶ from fecal samples collected on d 13. Quantification will be performed relative to ¹³C-butyrat, -acetate, or -propionate (internal standards), and normalized to fecal dry matter.

D. Detailed Study Procedures

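### PLS-DA is listed as a way to determine MFGM effects with no validation step; read from the fitted model at OTU level, it would appear to separate the two milks even with no effect

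*Combined protocol and SAP*

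**What the plan says.** Section III.C (Microbiota Composition) sets the sampling: "Microbiota composition will be assessed from fecal samples collected on d 13 of each study period". The features come from 16S sequencing, with "bacteria identified by comparing each operation taxonomic unit (OTU) to RDP and Silva databases". After the diversity measures, the plan continues: "followed by multivariate analysis (i.e. PCA, PERMANOVA, ANOSIM, PLS-DA) to determine MFGM effects".

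For PLS-DA the plan gives no input matrix, taxonomic level, OTU filter, number of components, cross-validation, hold-out set, error criterion or label-permutation test. It does not say which of the four methods decides if they disagree.

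The general analysis text in section III.B (Power Calculation and Data Analysis) assigns most data to mixed models with a random subject effect and adds "Significance for all analyses will be set at $P<0.05". Nothing there is specific to PLS-DA, PERMANOVA or ANOSIM. Section II (Anticipated Results) lists among the expected Objective 1 findings "an alleviation of gut dysbiosis (e.g. microbial diversity" and the Firmicutes:Bacteroidetes ratio.

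**The concern.** The four methods differ in kind. PCA ignores the treatment labels. PERMANOVA and ANOSIM test a group difference against a permutation reference. PLS-DA chooses weights for the taxa so that its scores line up with the labels, so separation is what it optimises. With few samples and many taxa, chance differences alone let it do this well. A score plot or classification rate from the fitted model is then not evidence of an effect unless it is checked on data that the model has not seen, or against the same procedure with labels swapped.

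The plan gives PLS-DA an inferential purpose and leaves that check out. If the fitted model were read directly, an apparent microbiota effect of MFGM could be put forward under Objective 1 when none exists. It could also sit beside a null PERMANOVA with no rule for which prevails.

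Respecting the crossover pairing does not solve this. Fitting PLS-DA to within-person differences still fits the labels.

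**Working it through.** **The plan's own figure.** None is given for the microbiota analysis. The only design figure is about 90% power for day-14 endotoxin with 14 completers, from a "conservative improvement of 60% of the difference in endotoxin in the MFGM vs control phases". The effect is (32.4 - 16.4) x 0.6 = 9.6 EU/mL. Taking the SD of 10.4 as that of the within-person difference, the noncentrality is 9.6 / (10.4 / √14) = 3.45 on 13 degrees of freedom. A two-sided paired t-test at 0.05 then has 89.1% power. The figure reproduces, and the present point does not touch it.

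**Number of samples (derived, not stated).**
- Enrolment, section III.A: "We will enroll male and female MetS adults (n = 24; 18-65 y".
- Attrition, section III.B: "This will also account for attrition (estimated at 10" percent.
- 24 x 0.9 = 21.6, about 22 completers; 22 x 2 = 44 samples (42 to 48 if 21 to 24 people complete).

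**Why the labels can be fitted from noise.** After centring, 44 samples span at most 44 - 1 = 43 dimensions. With 43 or more linearly independent features, some linear combination reproduces any labelling exactly. PLS-DA with a few components moves towards that fit.

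**Null simulations.** There were 22 people with two samples each and no treatment effect. Two components were assumed and features were scaled. The number of taxa is an assumption, so a range is shown. Model A uses log-normal taxa with multinomial counts, centred log-ratio transformed. Repeats of A with half the variance between participants agreed within 2 points. Model B uses sparse, correlated OTU counts after the same transform, with 0, 50% or 80% of the variance between participants.

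| Taxa | A: mean in-sample accuracy | B: mean in-sample accuracy |
|---|---|---|
| 10 | 64% | 60-68% |
| 20 | 74% | 65-74% |
| 50 | 88% | 73-85% |
| 100 | 98% | 81-90% |
| 300 | 100% | 92-97% |
| 1000 | not run | 99-100% |

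At 50 taxa under A, 0.88 x 44 is about 39 samples placed correctly, where chance gives 22. Independent Gaussian features gave 92-100% at 100 features and 100% at 300 or more.

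**How often the groups look apart.** As a yardstick only (the plan contains no such test), a t-test on the fitted scores gave P<0.05 in 100% of null runs at 100 or more features with 1, 2 or 3 components. With 2 components, the rate was 78-100% at 20 features and 13-96% at 10. With one component on model B, accuracy was 69-87% at 100 to 1000 OTUs: the groups shift apart but overlap.

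**Holding out whole participants.** With both samples of a person left out together, mean null accuracy was 47-53% in every setting run, which is chance.

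**Holding out one sample at a time.** Null accuracy was 16-38%, below chance. The person's other sample, which resembles the held-out one and carries the opposite label, stays in the training set and pulls the prediction the wrong way.

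**Within-person (multilevel) PLS-DA.** In one set of null runs, in-sample accuracy was 78% at 10 taxa, 99.7% at 50 and 100% at 100. These figures were not independently repeated.

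**Check of the proposed test.** Participant-wise 11-fold cross-validation, with a P value from within-person label swaps, rejected 1.5% of 200 null data sets (0.015 x 200 = 3) at a nominal 5%. It does not inflate false positives and may be conservative. Its power was not assessed.

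**The case against.** The plan is silent on how PLS-DA will be evaluated; it does not prescribe evaluation on the training samples. A reader might infer that the model will be judged on the same 44 samples and will therefore show separation almost every time. The documents do not support that as a statement of fact. The evaluation method is unstated, 44 is a derived count, and the frequency depends on taxa and component numbers that are not given. At about 10 taxa the false separation is far from certain.

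The list also reads as a toolbox. PCA, which tests nothing, stands under the same purpose clause, and PERMANOVA and ANOSIM are there to supply group-difference tests. A reader might go on to infer that a PLS-DA separation, with a ranking of the taxa behind it, would be reported as the MFGM effect. The plan mentions no such ranking. Its dysbiosis examples are microbial diversity and a phylum ratio, and neither rests on PLS-DA.

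These arguments limit the point but do not remove it. PLS-DA is still named for an inferential purpose, with no validation and no statement of which method decides. The gap is more than missing detail: reading the fitted model misleads at OTU level, and the common default of leaving out one sample at a time is wrong for paired samples.

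**Conclusion.** The point holds in conditional form. If PLS-DA is read from the fitted model at OTU level, it would appear to separate the milks in nearly all data sets with no MFGM effect, while its accuracy on participants not used in fitting is about 50%. This rests on about 22 completers, roughly 100 or more taxa, simulated rather than real 16S data and, for the accuracy figures, 2 components. It weakens with fewer taxa, and with one component the separation is partial.

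It is worth correcting before analysis but does not threaten the trial's main result. It concerns one tool for a secondary mechanistic outcome, and the primary day-14 endotoxin comparison and its power are unaffected.

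**What to change.** In section III.C (Microbiota Composition):

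- State that inference about a community difference between the milks rests on PERMANOVA with permutations restricted within participant.
- Label PCA and PLS-DA as descriptive.
- If PLS-DA is to support any claim, or any list of discriminating taxa, report only its accuracy with both samples of a participant held out together. Take the P value by swapping the milk labels within participants and repeating the whole cross-validation for each swap.

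The cost is a few sentences and some extra computing, with no extra samples or visits. The label-swap test may be conservative, and the PLS-DA result will probably look less favourable and may show no separation.

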and use of the restroom as needed. Urine will be collected during the 3 h postprandial period in the laboratory, and participants will be instructed on urine collection for when they return home following their laboratory visit. Participants will return to the study center the following day to drop off their 24-h urine collection tubes. To ensure that the order by which each participant completes each trial is randomized, a random sequence generator (<http://www.random.org/sequences/>) will be used to determine the order by which each participant will undergo the two trials.

Sugar Probe Test. On the morning of testing at day 14, participants will arrive at the study center after abstaining from food and only consuming water for 10-12 hours. A sugar probe test will be conducted as described.⁵⁶ Upon arrival, participants will be asked to empty their urinary bladder. Subsequently, they will then be asked to ingest a drink containing 1 g sucralose, 1 g erythritol, 1 g mannitol, and 5 g lactulose dissolved in 75 g glucose (240 mL). Within 2-hours after ingesting the sugar test beverage, participants will be asked to consume an additional 500 mL of water. Additionally, participants will be provided with standardized sucrose, erythritol, mannitol, and lactulose-free meals (e.g. bagel, peanut butter, scrambled eggs) during the 24-h period. All foods consumed during the 24-hour period will be free of artificial sweeteners. Urine will be collected from 0-5 and 6-24 hours in sterile containers. For each urinary collection period, participants will be provided 2-L urine collection bottles and an insulated reusable bag with ice packs to store collected urine until they return their samples the next day.

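### The two descriptions of randomization are not reconciled, and neither balances treatment order within gender; the cost is a small loss of precision in the gender analyses

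*Combined protocol and SAP*

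**What the plan says.** - **Study Design (III.A):** "They will be randomized in 4-unit blocks to receive" one of the two milks for 14 days, then the other after a washout. No stratification factor is named.
- **Detailed Study Procedures, Test trials (III.D):** a web-based random sequence generator "will be used to determine the order by which each participant will undergo the two trials". This text mentions neither blocks nor strata and does not refer back to III.A.
- **Power Calculation and Data Analysis (III.B):** the enrolment target is 24, made up of 12 women and 12 men. The sample is said to "provide sufficient power to consider gender x treatment interactions". The mixed model has "fixed effects for treatment, gender, time period, and their interactions", with a random effect for subject.
- **Intervention timeline (III.D):** the washout is two weeks. For women it is 2, 6, 10 or more weeks, so that testing falls at the same point of the menstrual cycle.

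No part of the protocol says that order is balanced within gender.

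**The concern.** Gender is both an enrolment quota and a planned effect modifier, but the randomization as written ignores it. The gap between periods can also be longer for women than for men, so a period effect could plausibly differ by gender. The model allows for this through its interactions. Once gender-by-period is fitted, each gender's treatment effect is estimated from the two orders within that gender, and its precision depends on how evenly those 12 people are split.

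The two descriptions also leave the scheme open. A team working from III.A would prepare blocks of four. A team working only from III.D could draw each order independently. The chance of an uneven split differs between these schemes, so the protocol should settle which one applies.

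**Working it through.** **1. The plan's own power figure.** Inputs from III.B: difference (32.4 − 16.4) × 0.6 = 9.6 EU/mL, SD 10.4, α = 0.05 (two-sided assumed), 14 completers. In a paired t-test with 10.4 taken as the SD of within-person differences, the noncentrality is 9.6/10.4 × √14 = 3.45 on 13 degrees of freedom. Power is 89.1%, which matches the stated figure of about 90%. The protocol does not label the SD; this reading reproduces its result and is used in step 5.

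**2. Variance cost of an uneven split.** With period fitted within gender, and orders split a:b among n people, the variance of the treatment effect relative to an even split is n²/(4ab). For n = 12:

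- 7:5 gives 144/140 = 1.029
- 8:4 gives 144/128 = 1.125
- 9:3 gives 144/108 = 1.333

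**3. Unstratified blocks of four (III.A).** Six full blocks give exactly 12:12 overall. Assume 12 women and 12 men, with gender unrelated to enrolment order. The number of women on a given order is then hypergeometric: P(x) = C(12,x)²/C(24,12), with C(24,12) = 2,704,156.

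| Split in women | Probability | Variance factor |
|---|---|---|
| 6:6 | 924²/2,704,156 = 0.316 | 1.000 |
| 7:5 | 2 × 792²/2,704,156 = 0.464 | 1.029 |
| 8:4 | 2 × 495²/2,704,156 = 0.181 | 1.125 |
| 9:3 | 2 × 220²/2,704,156 = 0.036 | 1.333 |
| 10:2 or worse | 0.003 | 1.8 or more |

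So 8:4 or worse has probability 22.0%, and 9:3 or worse 3.9%. A simulation of six blocks of four gave 21.9% and 3.9%. Weighting the factors by their probabilities gives 1.05, an expected variance inflation of about 5%, or about 2.5% in standard error. Because overall order is 12:12, men mirror women: 8:4 in one gender means 4:8 in the other, and both lose the same precision.

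**4. Independent draws (one possible reading of III.D).** From Binomial(12, 0.5):

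- 8:4 or worse in a given gender: 1,588/4,096 = 38.8%
- 9:3 or worse in a given gender: 598/4,096 = 14.6%
- 8:4 or worse in at least one gender: 1 − (1 − 0.388)² = 63%

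From Binomial(24, 0.5), overall order is 15:9 or worse with probability 30.7%. At 15:9 the variance factor is 576/(4 × 15 × 9) = 1.067.

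**5. Effect on the interaction test.** With 12 per gender, the standard error of the gender-by-treatment contrast is 10.4 × √(2 × factor/12). Power is for an assumed interaction of 9.6 EU/mL, on 20 degrees of freedom.

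| Split in both genders | Standard error (EU/mL) | Power |
|---|---|---|
| 6:6 | 4.25 | 58% |
| 8:4 | 4.50 | 53% |
| 9:3 | 4.90 | 46% |

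**6. If period were left out of the model.** An 8:4 split shifts a gender's treatment estimate by (8 − 4)/12 = 1/3 of the period effect. Mirrored splits would shift the interaction estimate by 2/3 of it. This does not arise if the model's time period is the crossover period.

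**The case against.** The strongest reply is that there is no conflict to resolve. III.A states the scheme and III.D names the tool. In any crossover the randomization sets each participant's order, and III.D never says that orders are drawn independently. This stands. A reader might infer that the protocol contradicts itself, or that 39%, 15% and 31% are the risks the trial runs. The text supports neither inference. Those figures belong to an unconfirmed reading, and under the only scheme stated by name they become 22%, 3.9% and zero.

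A reader might also infer that uneven order confounds treatment with period and biases the result. Everyone receives both milks and the plan fits a period term with interactions, so the loss is precision, not bias, if that term is the crossover period.

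The reply can add three further points, all fair:

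- The gender analysis is secondary, since the sample size rests on the overall treatment effect.
- The investigators' earlier repeated endotoxin data showed no difference by time or gender (P above 0.4).
- Sample size limits the interaction test more than order does: power is 58% even at 6:6, and 19% for an interaction half as large. Stratification does not cure that.

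Two points remain. III.A and III.D do not refer to each other, and blocks of four without strata still leave order within gender to chance. Leaving a 24-person crossover unstratified is a legitimate choice. Here, however, the quota and the planned contrast make stratification almost free.

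**Conclusion.** The point holds as a minor one. The two randomization statements are unreconciled rather than contradictory, and neither balances order within gender. Under unstratified blocks of four, the expected variance inflation within a gender is about 5%, with a 22% chance of a split that costs 12.5% or more. Under independent draws the chance in a given gender would be 39%.

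The affected quantities are the gender-specific and interaction estimates. Under blocks, the primary endotoxin comparison is essentially unaffected.

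The conclusion rests on these assumptions:

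- 12 women and 12 men are randomized.
- Gender is unrelated to enrolment order. If whole blocks were of one gender, the imbalance would disappear.
- The model's *time period* is the crossover period, and its interaction with gender is fitted.
- For the power figures only, 10.4 EU/mL is the SD of paired differences.

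**What to change.** Use the same statement in III.A and in the Test trials text of III.D: the sequence generator builds permuted blocks of four separately for women and for men. Three blocks per gender fill 12 and 12 exactly and give 6:6 order in each at randomization. In III.B, state that *time period* means the crossover period.

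The cost is two short lists instead of one, with no added participants. Balance among completers is not guaranteed. The expected 10% attrition (about 2 of 24) may disturb it, and a block stays incomplete if a gender target is missed. If the investigators prefer not to stratify, one sentence in III.D saying that the generator produces the blocks of four described in III.A would at least settle which scheme applies.
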